11.8. Causality

For all adverse events, the investigator must pursue and obtain adequate information to determine the outcome of the adverse event and to assess whether the AE meets the criteria for classification as an SAE, serious suspected adverse reaction, suspected adverse reaction, unexpected AE, or unexpected suspected adverse reaction. For all AEs, sufficient information should be obtained by the investigator to determine the causality of the AE. For AEs with a causal relationship to the IP or the enema procedure, follow-up by the investigator is required until the event or its sequelae resolve or stabilize at a level acceptable to the investigator.

The investigator will make a causality assessment for all AEs and decide whether there is a reasonable possibility that the AE may have been caused by the study product or procedure, including an assessment of biologic plausibility, presence or absence of alternative causal explanations (such as continuation or exacerbation of the subject's recurrent CDI symptoms), and temporal relationship to product administration and/or the procedure. Relatedness to RBX2660 or the enema procedure is defined as:

- Unrelated: The event is due to an underlying or concurrent illness or effect of concomitant therapy and is not related to the study product or procedure (*e.g.*, has no temporal relationship to study product or procedure, or has a much more likely alternative etiology)
- Possible: There is some temporal relationship between the event and the administration of the study product or procedure, though the event could also be explained by the subject's medical condition or other therapies.
- Probable: The temporal relationship between the event and administration of the study product or procedure is suggestive, and the event is unlikely to be explained by the subjects' medical condition or other therapies alone.
- Definite: The event follows a reasonable temporal sequence from administration of the study product or procedure, follows a known or suspected response pattern to the study product and/or procedure, improves upon stopping the study product, and reappears upon repeated exposure, if that occurs.

If an investigator is unsure about whether to report a finding as an AE, they are encouraged to enter the finding as an AE into the study database.

11.9. Pregnancy Reporting

If the subject or partner of a subject participating in the study becomes pregnant during the study after IP administration, the investigator should report the pregnancy to Medpace Clinical Safety within 24 hours of being notified. Medpace Clinical Safety will then forward the Exposure In Utero form to the investigator for completion.

The subject or partner should be followed by the investigator until completion of the pregnancy. If the pregnancy ends for any reason before the anticipated date, the investigator should notify Medpace Clinical Safety. At the completion of the pregnancy, the investigator will document the outcome of the pregnancy. If the outcome of the pregnancy meets the criteria for immediate classification as an SAE (i.e., postpartum complication, spontaneous abortion, stillbirth, neonatal death, or congenital anomaly), the investigator should follow the procedures for reporting an SAE.

11.10. Medical Monitor

An independent Medical Monitor reviews all SAEs and other events reported by the site as related to the investigational product or enema procedure to provide an objective, qualified judgment of the events. The Medical Monitor is a physician not participating as an investigator in this study. The Medical Monitor has the responsibility to review and evaluate the information relevant to product safety throughout the development and implementation of the protocol. The Medical Monitor performs the following functions:

- Reviews SAEs and other AEs as requested;
- Reviews the study protocol and Investigator's Brochure for adequacy of safety oversight;
- Confers with site investigators, DSMB and the Rebiotix Clinical Department as applicable regarding potential safety concerns;
- Provides medical surveillance and provides appropriate recommendations for the conduct of the study as needed.

Details of the Medical Monitor activities and expectations will be documented in a Safety Management Plan.

11.11. Data and Safety Monitoring Board (DSMB)

The DSMB will consist of at least two physicians specializing in infectious diseases or gastroenterology who have experience managing subjects with recurrent CDI and are not investigators in the study. A biostatistician who is not involved with study design or analyses may assist the DSMB. The DSMB will operate in accordance with applicable

sections of the FDA Guidance for Clinical Trial Sponsors *Establishment and Operation of Clinical Trial Data Monitoring Committees*.

Details of the DSMB logistics, activity and responsibilities will be included in a DSMB charter. General responsibilities include oversight of subject safety through data review and assessment of trends. This includes the ability to stop the study based on protocol-defined stopping rules. Additionally, the DSMB may provide an independent review of the efficacy outcome to ensure the benefits of providing this treatment to subjects outweighs the risks.

11.12. Endpoint Adjudication Committee (EAC)

The EAC will provide independent adjudication of treatment success or failure that will be used for study analysis and reporting purposes. The EAC will be comprised of three physicians specializing in infectious diseases or gastroenterology who have experience managing subjects with recurrent CDI and are not investigators in the study. Details of the EAC logistics, activity and responsibilities will be included in an EAC charter.

11.13. Study Stopping Rules for Safety

Rebiotix will oversee review of all AEs reported during the study to observe for trends and unanticipated events, either in severity, seriousness or incidence, and to assess if a study stopping rule may be triggered. AE review includes the event description, onset date in relation to the treatment date, and the investigator's determination of causal relatedness to IP, the enema procedure, and pre-existing condition, as well as rating the event's severity and seriousness. Additionally, the Medical Monitor assessment of seriousness and causality will be provided and reviewed as it may be different from the site investigator report of the event. Anticipated AEs may trigger the study stopping rules.

The DSMB will determine whether enrollment should be paused, the study terminated, or other actions taken based on their assessment that:

- a) There is probable cause that IP or enema procedure (e.g., due to transfer from an RBX2660 donor) contributed to a pathogenic intestinal infection in the stool of any subject, or
- b) Any events of major significance such as death or other serious outcome for which a causal connection with the IP is plausible and represents an excess of the important adverse event(s).

To support the DSMB assessment, the Rebiotix Operations Department may be asked to review the donor history and batch processing/release records for the product unit(s) administered in these cases, and forward its report to the DSMB Chair for review. The DSMB Chair will review the Operations Department report. If probable cause is suspected, the DSMB Chair will convene the entire DSMB for event review.

Upon the DSMB's determination of action, the Chair will notify Rebiotix, who will notify the study sites.

If enrollment is stopped, Rebiotix and the study sites will assess for the occurrence of similar events, and evaluate IP and study records for possible root cause(s). Enrollment may be re-started upon further review and approval from the DSMB. As appropriate, the DSMB may recommend study termination or measures short of termination with the objective of reducing the risk of AEs.

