Statistical Considerations	The primary safety analysis will be performed on all subjects exposed to RBX2660 and will include descriptive statistics. Additional sub-analyses of safety data may be performed on sub-populations. Efficacy analyses will be performed on pre-defined analysis populations including Intent-to-Treat (ITT) and modified Intent-to-Treat (mITT). A final analysis of safety and efficacy results will be analyzed and reported in a final report after the last subject has completed the 6-month follow-up visit for their study treatment, including 6-month follow-up after a second RBX2660 study treatment, if applicable.

Study Stopping Rules	
The DSMB will determine whether enrollment will be paused, the study terminated, or other action taken based on their assessment that:
 
• There is probable cause that the IP or enema procedure (e.g., due to transfer from an RBX2660 donor) contributed to a new pathogenic intestinal infection in the stool of any subject; or• Any events of major significance such as death or other serious outcome for which a causal connection with the IP is plausible and represents an excess of the important adverse event(s). 
In the event that one of the preceding rules appears to be met based on site reported data and/or Medical Monitor review, the Rebiotix Operations Department will review the donor history and batch processing/release records for the product unit(s) administered in these cases. A report of the review will be forwarded to the DSMB Chair for review. If probable cause is suspected, the DSMB Chair will convene the entire DSMB for event review.
 
Upon the DSMB's determination of action, the Chair will notify Rebiotix, who will notify the study sites. If enrollment is stopped, Rebiotix and the study sites will assess for the occurrence of similar events and evaluate IP and study records for possible root cause(s). Enrollment may be re-started upon further review and approval from the DSMB. As appropriate, the DSMB may recommend study termination or measures short of termination with the objective of reducing the risk of adverse events. Details regarding DSMB responsibilities will be provided in the DSMB Charter.

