5.4.3.3 Relationship of Adverse Events to Study Treatment

Relationship of an AE to the Investigational Product (IP), the enema procedure, *C. difficile* disease, and a preexisting condition will be classified by the investigator as definite, probable, possible, or unrelated. Related events will include AEs that are classified as definitely, probably, or possibly related.

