7.5.1 Study Stopping Rules

Enrollment will be paused if any of the following events are identified and the DSMB determines that there is probable cause that the IP or enema procedure contributed to the event:

1. There is probable cause that IP or enema procedure (e.g., due to transfer from an RBX2660 donor) contributed to a pathogenic intestinal infection in the stool of any subject, or
2. Any series of events of major significance such as death or other serious outcome for which a causal connection with the IP is plausible and represents an excess of the important adverse event(s).

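### Stopping rule (b) names only the IP as the cause of serious outcomes, so an excess of serious non-infectious harm from the enema procedure alone meets neither written rule

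*Protocol*

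**What the plan says.** Rule (b) appears in three places, each time with the IP as the only named cause:

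- Protocol 11.13 (b): "Any events of major significance such as death or other serious outcome for which a causal connection with the IP is plausible", with the further condition that the events represent an excess.
- Protocol synopsis, Study Stopping Rules: "other serious outcome for which a causal connection with the IP is plausible and represents an excess".
- SAP 7.5.1 item 2: "causal connection with the IP is plausible and represents an excess of the important adverse event(s").

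Rule (a), beside it in each place, names both the IP and the enema procedure but is confined to a pathogenic intestinal infection. The SAP adds a lead-in covering both items, under which enrollment is paused if "the DSMB determines that there is probable cause that the IP or enema procedure contributed to the event".

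Elsewhere the product and the procedure are separate causes. SAP 5.4.3.3 has the investigator classify each one: "Relationship of an AE to the Investigational Product (IP), the enema procedure", along with *C. difficile* disease and preexisting condition. The primary endpoint (Protocol 6.4) counts subjects with TEAEs related to the product, the enema, or both. The adverse event review in Protocol 11.13, done partly to see whether a stopping rule may be triggered, includes the investigator's "determination of causal relatedness to IP, the enema procedure, and pre-existing condition".

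**The concern.** A stopping rule tells the DSMB, the sponsor and the sites in advance which pattern of harm calls for a formal decision. Here the rule for death and serious outcomes covers less than the harm counted in the primary endpoint. It also covers less than the relatedness data that Section 11.13 has reviewed in order to apply it. If serious injuries accumulated from placing the rectal tube, with a link to the suspension itself judged implausible, the DSMB would have to act on general judgement because no named rule would apply.

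The wording also affects escalation. Protocol 11.11 describes the DSMB's ability to stop the study as resting on the protocol-defined rules. In the synopsis, the sequence of Operations review, Chair review and convening of the full board begins when one of the rules appears to be met.

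**Working it through.** The rules are qualitative, with no event count, boundary or error rate, so the check is mainly a reading of the text.

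**1. Scope of each rule**

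| Rule | Cause named | Harm covered |
|---|---|---|
| (a): synopsis, Protocol 11.13, SAP item 1 | IP or enema procedure | Pathogenic intestinal infection only |
| (b): synopsis, Protocol 11.13, SAP item 2 | IP only | Death or other serious outcome, in excess |
| SAP 7.5.1 lead-in | IP or enema procedure | Whatever items 1 and 2 list |

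**2. Test cases**

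- Intestinal infection with probable cause in the procedure: rule (a) applies.
- Excess of serious non-infectious events with a plausible IP link: rule (b) applies.
- Excess of serious non-infectious events attributed to the procedure, IP link judged implausible: rule (a) fails on the type of harm and rule (b) fails on the cause.

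**3. Does the SAP lead-in close the gap?** An event must be one of the listed items and also satisfy the lead-in. The lead-in accepts either cause, but item 2 still requires a plausible IP connection. The two conditions together still require the IP link. The lead-in suggests that the procedure was meant to be covered; it does not change item 2.

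**4. Can IP be read to include the procedure?** Not easily. SAP 5.4.3.3 rates them separately, SAP 6.6.2.1 tabulates them separately, and the adjacent rule (a) names both.

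**5. Is the third case foreseeable?** Protocol 11.3 lists intestinal puncture among the anticipated events, and Protocol 11.13 says that anticipated events may trigger the rules.

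**6. What earlier studies show about procedure attribution**

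- Study 2019-02 (Protocol 5.3.5). The denominator follows from the SAE line: 8 / 0.125 = 64. Check: 3/64 = 4.69% and 11/64 = 17.19%, matching the printed 4.7% (enema-related) and 17.2% (IP-related). The overlap is not given. If all 3 enema-related subjects are among the 11 IP-related ones, 0 are procedure-only; if none is, 3 are. The range is 0/64 to 3/64, or 0% to 4.7%. All SAEs were judged unrelated to both, so none of these related events was serious.
- Study 2017-01 (Protocol 5.3.4). Of 54 serious TEAEs, 0 were related to the procedure and 0 to the IP.
- Study 2015-01 (Protocol 5.3.3). One death was reported as possibly related to the IP or the procedure, and definitely related to *C. difficile* disease and pre-existing conditions. The two study causes are pooled, so this death cannot be counted for or against the uncovered case.

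These figures show that attribution to the procedure does occur. They do not give a rate of serious procedure-only harm.

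**The case against.** The best case for leaving the text alone is that nothing practical turns on it. To fall outside both rules, an event must be serious, non-infectious, in excess, attributed to the procedure, and have an IP link that is not even plausible. The product is given only by enema, and its kit includes the rectal tube. Protocol 11.3 itself says that the anticipated events, puncture included, may or may not be related to the IP, the procedure or CDI. A rule aimed at the product also fits the donor and batch review that follows it, and the protocol regards enema risk as low. A stopping rule need not match the primary endpoint.

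There are backstops too. The Medical Monitor reviews all SAEs and events reported as procedure-related, passes that review to the DSMB, and can recommend changes to study conduct. On the DSMB, Protocol 11.11 says "General responsibilities include oversight of subject safety through data review and assessment of trends", and Protocol 11.13 adds that "the DSMB may recommend study termination or measures short of termination with the objective of reducing the risk of AEs". The charter is not among the documents and may say more.

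Most of this stands as a limit on importance: the case is rare, and the DSMB could respond to it. It does not remove the gap. Mechanical injury is the clearest case where a procedure link is evident and an IP link may be rejected. The sentence on recommending termination sits in the paragraph about what follows once enrollment has stopped. Protocol 11.11 ties the named stopping power to the protocol's own rules. An unseen charter cannot be assumed to widen them.

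**Conclusion.** The concern holds as a minor inconsistency in wording. As written, an excess of serious non-infectious harm attributed to the enema procedure alone meets neither stopping rule in the synopsis, Protocol 11.13 or SAP 7.5.1. Such harm would still reach the Medical Monitor and the DSMB, so it would not go without a response; what is missing is a named rule to act on.

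No reported event can be identified as being of the uncovered kind, and its frequency cannot be estimated. No estimate, endpoint or analysis changes. The conclusion assumes a literal reading of IP as the product, consistent with the separate relatedness ratings, and that the DSMB charter does not already extend the rule.

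**What to change.** In the synopsis, Protocol 11.13 (b) and SAP 7.5.1 item 2, insert *or enema procedure* after IP, so that the rule requires a plausible causal connection with either. Keep the condition that the events represent an excess, so that a single procedural event does not automatically pause enrollment.

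This is three words in three places at the next amendment, in line with the SAP's own lead-in. It needs no new data, staff, committee or analysis. The only likely burden is an occasional extra DSMB review of a procedural event. If the charter repeats the rule, it should be brought into line at the same time.

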11.14. Sponsor Reporting of Adverse Events

The sponsor will report all relevant information about suspected unexpected serious adverse reactions that are fatal or life-threatening as soon as possible to the FDA & Health Canada, and in any case no later than seven (7) days after knowledge by the sponsor of such a case, and that relevant follow-up information will subsequently be communicated within an additional eight (8) days.

All other suspected unexpected serious adverse reactions will be reported to the FDA as soon as possible but within a maximum of 15 days of first knowledge by the sponsor.

The sponsor will also inform all investigators as required.

11.14.1. Timeline for Reporting Requirements

The following describes the expedited safety reporting requirements by timeline for reporting and associated type of event:

- Within 7 calendar days of event discovery by Rebiotix

Rebiotix will notify FDA and Health Canada of any unexpected fatal or life-threatening suspected adverse reaction as soon as possible but in no case later than seven (7) calendar days after the sponsor's initial receipt of the information.

- Within 15 calendar days of event discovery by Rebiotix

The AE must meet all three of these criteria for expedited reporting. Any study event that is:

- suspected adverse reaction
- serious
- unexpected

11.14.2. Additional Reporting Requirements

The sponsor will identify in IND safety reports all previous reports concerning similar AEs and analyze the significance of the current event in light of the previous reports.

11.14.3. Reporting AEs to FDA and Health Canada

Rebiotix will report AEs to FDA and Health Canada as required by applicable regulations. All AEs will be reported in the annual and final clinical study reports.

12. Sample Size and Statistical Considerations

This study has a Statistical Analysis Plan which contains complete details of the statistical methodology and analyses that will be employed for this study. A final analysis of safety and efficacy results will be analyzed and reported in a final report after the last subject has completed the 6-month follow-up visit for their study treatment, including 6-month follow-up after a second RBX2660 study treatment, if applicable.

12.1. Sample Size

The purpose of this study is to assess the safety and tolerability of RBX2660 in a recurrent CDI population that is broader and more inclusive than that included in prior studies using RBX2660. In order to continue to collect prospective safety information and allow open-label treatment access to a broad population of patients, up to 750 subjects will be treated with RBX2660.

Subjects who have signed informed consent forms but do not meet all eligibility criteria will be considered screen failures. Subjects who withdraw for any reason prior to administration of the enema will be replaced without counting toward the sample size treatment cap of 750 subjects.

12.2. Assessment of Safety and Tolerability

Assessment of the primary safety objective and other safety objectives will be performed on all subjects exposed to RBX2660 (Safety Population) and will include descriptive

statistics. Additional sub-analyses of safety data may be performed on sub-populations (e.g., subjects with irritable bowel disease or irritable bowel syndrome).

12.3. Assessment of Efficacy, Secondary Objectives

Assessment of secondary objectives will include descriptive statistics and be performed on pre-defined analysis populations including Intent-to-Treat (ITT), modified Intent-to-Treat (mITT) and Per-Protocol (PP). Additional sub-analyses of safety data may be performed on sub-populations.

Secondary Efficacy Endpoints:

1. Recurrence of CDI within 8 weeks of treatment.

Recurrence of CDI after 8 weeks from completion of the study treatment is considered a new CDI.

The efficacy parameter used to determine treatment success is defined as the absence of CDI diarrhea through 8 weeks after completing a study treatment. Efficacy assessments will occur at each scheduled contact: 1-, 4- and 8-weeks.

2. Loss of sustained clinical response through 6 months after treatment

Sustained clinical response is defined as treatment success of the presenting CDI recurrence and no new CDI episodes through 6 months after completing a study treatment. Efficacy assessments will occur at each scheduled contact: 4 and 6 months.

12.3.1. Analysis Population definitions

12.3.1.1. Safety Population

The safety population (SP) is defined as the population of subjects who had any treatment attempted or completed. The safety population will be used in analysis of all safety endpoints including the primary endpoint.

